Study ID: I15600-003

Samsca drug use-results survey (ADPKD) Study Protocol

NCT Number: NCT02847624

Otsuka Pharmaceutical Co., Ltd.

Protocol Creation Date: February 21, 2014, Version 1.0 Date of the latest version: September 2, 2021, Version 8.0

Objective of	To determine the safety and efficacy of Samsca used in routine clinical settings for suppression of
survey	ADPKD progression.
Survey	<all patients="" survey=""></all>
methods	All patients treated with Samsca must be registered in the survey until "CONDITIONS FOR
	APPROVAL" is removed.
	CRFs must be collected from all patients until the total number of patients registered in the survey
	reaches the planned number.
	Observation period: From start of Samsca administration through the end of survey
	In case of finish or discontinue of Samsca administration, collecting information of kidney
	volume, changes in renal function and hepatic dysfunction (outcome: not recovered) through
	the end of survey (8 years).
Survey period	8 years (March 24,2014 ~ March 23,2022)
Planned	1,600
number of	Depending on the onset of significant drug-induced liver injury post-marketing, the planned
patients to be	number of patients will be re-evaluated and necessity of additional safety measures will be also
surveyed	assessed.
	In addition, if there is a substantial change in expected number of patients with long-term
	treatment (≥4 years), the planned number of patients will be re-evaluated so as to collect at least
	800 patients with long-term treatment.
Target patient	All patients treated with Samsca after March 24, 2014 for the indication of "suppression of
population of	ADPKD progression with a rapid kidney volume increase in patients with increased kidney
• •	volume"
Major items to	1
	CRFs of drug use-results survey (for treatment period) 1) Patient information
be surveyed	
	Patient initials (last name, first name), patient ID, sex, any breast feeding, any pregnancy,
	date of birth (age), date of informed consent received (in written form)
	2) Patient demographics
	Indication for use, time of ADPKD diagnosis, diagnosis of ADPKD (severity of ADPKD,
	family history, number of cysts, complications (especially, hepatic cyst, pancreatic cyst,
	cerebral aneurysm, urinary calculus, any complication of cyst infection), past history,
	predisposition to hypersensitivity, history of drug adverse reactions
	3) Administration status of Samsca
	Dosage form, time and dose, route of administration, period of administration (date started,
	date stopped),
	4) Usage status of Samsca
	Ongoing, completed, discontinued (reason for discontinuation → adverse events,
	insufficient efficacy, changing hospital, other), no visit
	5) Changes in kidney volume
	5) Changes in kidney volume In-patient/out-patient status, total kidney volume (measured or not, method of
	In-patient/out-patient status, total kidney volume (measured or not, method of

Height, weight, body temperature, ECG finding

(3) Blood chemistry tests

AST (GOT), ALT (GPT), e-GFR

(4) Urinalysis

Urinary protein, urine sugar, bilirubin, urobilinogen, urine albumin, urine osmolality

7) Adverse events after start of Samsca administration

Specific adverse events, onset date, seriousness, reason for seriousness (if serious), date of outcome assessment, outcome, causal relationship to Samsca, other causative factors than Samsca, corrective treatment for adverse event

8) Condition around the event onset

Condition around the event onset, comments on the adverse events

CRFs of drug use-results survey (for follow-up period)

1) Patient information

Patient initials (last name, first name), patient ID, sex, any breast feeding, any pregnancy, date of birth (age), date of informed consent received (in written form)

2) Changes in kidney volume

In-patient/out-patient status, total kidney volume (measured or not, method of measurement), change of kidney volume,

- 3) Laboratory values
 - (1) Physical examination Height, weight
 - (2) Blood chemistry tests

AST (GOT), ALT (GPT), e-GFR

4) Follow-up investigation of adverse events that remained unresolved or were of unknown status during the treatment period.

Specific adverse events, onset date, seriousness, reason for seriousness (if serious), date of outcome assessment, outcome, causal relationship to Samsca, other causative factors than Samsca, corrective treatment for adverse event

5) Condition around the event onset and comments on the adverse events

Items to be CRFs of drug use-results survey (for treatment period) analyzed 1) Items related to constitution of patients Number of patients enrolled, number of patients withdrawn, number of CRFs collected, number of patients excluded, number of patients analyzed for safety, number of patients analyzed for efficacy 2) Items related to efficacy Changes in kidney volume data, changes in renal function test data (e-GFR) 3) Items related to safety (1) Safety in elderly patients (2) Safety of Samsca in advanced ADPKD patients (creatinine clearance <60 mL/min) (3) Adverse events of special interest (hepatic dysfunction, increases in transaminases (AST or ALT)) (4) Items to be closely monitored: hepatic dysfunction (5) Safety of Samsca in ADPKD patients after long-term treatment CRFs of drug use-results survey (for follow-up period) 1) Changes in kidney volume, changes in renal function test data (e-GFR)

1.1. Terms

Terms	Definition
Adverse event	An adverse event refers to any undesirable medical occurrence that has happened to a patient who has been administered a pharmaceutical product, and it does not necessarily only refer to those with a causal relationship with the administration of the said pharmaceutical product. In other words, an adverse event refers to any undesirable, unintended sign (for example, abnormal clinical test values), symptom, or disease that is temporally related to the use of a pharmaceutical product, regardless of whether there is a causal relationship with the said pharmaceutical product. For the notation of organ-specific major classifications and symptom names, etc., the latest version of "MedDRA/J" at the time of reporting is used.
Adverse Drug Reaction (ADR)	Among the adverse events, those that have been determined to have an undeniable causal relationship with this drug (excluding "no causal relationship"). For the notation of organ classification and symptom names, the latest
	version of "MedDRA/J" at the time of reporting is used.
Serious adverse event	 Death Disability: A state indicating the manifestation of functional impairment to the extent that it interferes with daily life. Risk of death: Symptoms that may lead to death: Cases where the patient was exposed to the risk of death when ADRs or infectious diseases occurred. This does not imply a hypothetical meaning that if the ADRs or infectious diseases were more severe, it could have led to death. Risk of disability: Symptoms that may lead to disability: Depending on the patient's constitution, it refers to symptoms that may lead to functional impairment to the extent that it interferes with daily life. Hospitalization or extension of hospital stay: Symptoms requiring hospitalization or extension of hospital stay was required for the treatment of ADRs or infectious diseases. It does not include hospitalization or extension of hospital stay for testing. Also, hospitalization for observation of the course of ADRs or infectious diseases that are healing or improving does not apply. Serious as per 1-5: Symptoms that are serious in accordance with 1 to 5: Refers to serious symptoms that require measures to prevent outcomes like those in 1 to 5. Congenital anomalies, etc.: Congenital diseases or abnormalities in future generations: Cases suspected of causing abnormalities in newborns due to exposure to drugs before or during pregnancy apply.

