As shown in Table 3, for the post-marketing surveillance, the number of survey cases and the number of cases with serious adverse events are aggregated, and the incidence rate of serious adverse events is calculated. In addition, frequency aggregation by SOC and PT is performed, and the incidence rate is calculated. In the PT-specific aggregation, events where the causal relationship has been denied (unrelated) are also aggregated, but if there are events that are related and events where the causal relationship has been denied in the same PT in the same case, the related events are prioritized and not counted as events where the causal relationship has been denied.

In addition, similar aggregation is performed for serious ADRs, but aggregation of events where the causal relationship has been denied is not performed in the PT-specific aggregation.

Table 3. Overview of the Occurrence Status of Serious Adverse Events

Item Name	Definition content
Severity	Adopt the severity determined by the physician.
Causal Relationship	Adopt the causality determined by the physician.
Case Number	The case numbers used to count the number of survey cases and the number of cases with ADRs, etc., are as follows: ADPKD: Patient-specific number (BaseEntryNO)
Number of Cases investigated	Aggregate the number of cases for safety analysis.
Number of cases with adverse event occurrence	If multiple serious adverse events occur in the same case, it is counted as one case.
Incidence Rate of adverse event, etc.	Number of cases with adverse event occurrence / Number of cases subject to safety analysis x 100
Major Classification by Organ	MedDRA SOC (name)
Basic or Subordinate Terms	MedDRA PT (name)

^{*}Display order: SOC international agreement order, PT code ascending order

Item Name		Definition content
Incidence Rate by SOC, PT		SOC: Number of cases with ADRs / Number of cases for safety analysis x 100 PT: Number of cases with ADRs / Number of cases for safety analysis x 100
ADPKD	Usage Performance Survey (Post-Marketing Cases)	Target all cases for safety analysis.
Examination Item Name1		Name assigned from safety review items.
Examination Item Name2		Name assigned from safety review items. If there is a name different from the examination item name 1, output it.

2.3.2.1. Duration until ALT and AST exceed the upper limit of the reference value

[Analysis Target]

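### SAP Table 3 computes the SOC and PT rates of serious adverse events from ADR cases, contradicting the 2.3.2 text and the table's own overall rate

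*SAP*

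**What the plan says.** SAP 1.1 defines an adverse event as any undesirable occurrence "regardless of whether there is a causal relationship with the said pharmaceutical product". ADRs are a subset: "Among the adverse events, those that have been determined to have an undeniable causal relationship with this drug".

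SAP 2.3.2 sets out two tabulations. In the first, "the number of survey cases and the number of cases with serious adverse events are aggregated", with a breakdown by SOC and PT. At PT level "events where the causal relationship has been denied (unrelated) are also aggregated". A patient with both a related and an unrelated event under one PT is counted as related only. The second tabulation covers serious ADRs and leaves the unrelated events out.

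Table 3, titled for serious adverse events, gives the formulas:

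- **Overall rate:** cases with an adverse event, divided by the safety analysis cases. The counting row shows that serious adverse events are meant, with several in one patient counted once.
- **Class-level rate:** "SOC: Number of cases with ADRs / Number of cases for safety analysis x 100". The PT line has the same numerator.
- **Seriousness and causality:** both are taken from the physician. The seriousness row is labelled as severity.

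Two of the seriousness criteria in SAP 1.1 are worded for a narrower set of events. Risk of death reads: "Cases where the patient was exposed to the risk of death when ADRs or infectious diseases occurred". Hospitalisation applies where a "hospital stay was required for the treatment of ADRs or infectious diseases". Death, disability, risk of disability, the criterion for events as serious as items 1 to 5, and congenital anomaly carry no such limit.

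**The concern.** A PT row cannot include events judged unrelated and also be computed from ADR cases alone, because ADRs exclude those events by definition. Nor can the overall row and the SOC and PT rows of one table be read together when they count different things. Whoever programs Table 3 must choose between the text and the formula, and the SAP does not say which governs.

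Safety is a stated objective of the survey, and the survey has no comparator. The all-cause breakdown of serious events by SOC and PT is useful because it does not rest on each physician's attribution. An ADR numerator brings that dependence back. As written, it also drops the restriction to serious events.

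**Working it through.** The documents state no serious event rate, so there is no figure to reproduce. The check sets the passages side by side and then works out what each reading of the numerator would print.

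**1. What each place counts**

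| Place in SAP | Events counted | Unrelated included? | Serious only? |
|---|---|---|---|
| 2.3.2 text, first tabulation | serious adverse events | yes, stated for PT | yes |
| 2.3.2 text, second tabulation | serious ADRs | no | yes |
| Table 3, overall rate | adverse event cases (serious, by the counting row) | yes | yes |
| Table 3, SOC and PT rates | ADR cases | no | not stated |

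The last row disagrees with the first on causality and, read literally, on seriousness. Table 2 in 2.3.1.1, which is titled for ADRs, has the same SOC and PT wording.

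**2. Formulas for one SOC or PT**

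- a = patients with a related serious event
- b = patients whose serious events there were all judged unrelated
- c = patients with a non-serious ADR and no serious event there
- N = safety analysis cases

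The three rates are:

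- intended by the text: (a + b) / N
- numerator read as serious ADRs: a / N
- numerator read literally as ADR cases: (a + c) / N

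Patients with both an unrelated serious event and a non-serious ADR in the same SOC or PT are left out for simplicity. They would add equally to the intended and literal counts.

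The literal rate minus the intended rate is (c − b) / N. It is too low when c < b, right by coincidence when c = b, and too high when c > b. On the serious-ADR reading the relative shortfall is b / (a + b), the unrelated share.

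**3. Illustration**

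N = 1,600 is the protocol's planned number, used here as the size of the safety set. The 80 serious cases, the related shares and the values of c are assumptions. The intended rate is 80 / 1,600 = 5.00% throughout.

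| Related share | a | b | Serious-ADR reading, a/N | Literal, c = 0 | Literal, c = b | Literal, c = 160 |
|---|---|---|---|---|---|---|
| 25% | 20 | 60 | 1.25% | 1.25% | 5.00% | 11.25% |
| 50% | 40 | 40 | 2.50% | 2.50% | 5.00% | 12.50% |
| 75% | 60 | 20 | 3.75% | 3.75% | 5.00% | 13.75% |
| 100% | 80 | 0 | 5.00% | 5.00% | 5.00% | 15.00% |

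For example, at 50% related with c = 160: (40 + 160) / 1,600 = 12.50%.

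**4. What is not affected**

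The overall serious adverse event rate has its own numerator, so none of this changes it.

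**5. The wording in SAP 1.1**

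Read alone, a hospitalisation for a non-infectious event judged unrelated would not meet the hospitalisation criterion. An unrelated infection would. Whether any count changes depends on how physicians rated seriousness. The protocol's list of survey items collects seriousness, the reason for it and the causal relationship as separate fields, and Table 3 adopts the physician's determination. Nothing in 2.3.2 tells the analyst to re-derive seriousness from 1.1. No number can be attached to this part.

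**The case against.** The best defence is that the ADR wording is a carried-over label. Table 2 has the identical SOC and PT lines, the case-number row of Table 3 also speaks loosely of ADRs, and the same specification is to serve the serious ADR table. The text beside the table states the all-cause intent and even gives a rule for mixed cases. On this view a programmer would follow the text and nothing would be misstated. That is a plausible account of how the wording arose, but it leaves the SAP with a formula that contradicts its text and no statement of which prevails.

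A reader might also infer more than the documents support:

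- **That the SOC and PT rates would be understated.** This follows only if the numerator is taken to mean serious ADRs. The literal wording also admits non-serious ADRs, which can push a rate above the intended one.
- **That all-cause serious event rates disappear.** They do not. The overall rate counts adverse event cases, and the text plans for unrelated events at PT level.
- **That SAP 1.1 makes unrelated hospitalisations non-serious in the analysis.** Seriousness comes from the physician, separately from causality. The criterion for events as serious as items 1 to 5 has no explicit ADR limit, although it refers back to the two restricted items. The documents do not show that physicians applied the narrow wording to unrelated events.

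The objection succeeds on direction, on the overall rate and on the weight of the 1.1 wording. It does not remove the conflict in Table 3.

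**Conclusion.** The point holds as an internal contradiction in a stated analysis formula. The SOC and PT numerators of Table 3 do not match the serious adverse event tabulation that 2.3.2 describes, nor the table's own overall rate. If the formula is followed, those rates are off by (c − b) / N, and the documents settle neither sign nor size. If it is read as serious ADRs, they are low by the unrelated share, which the documents do not give. The percentages above are illustrations on assumed counts and are not estimates for this survey.

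The risk-of-death and hospitalisation wording in 1.1 is a secondary inconsistency with the all-cause adverse event definition, of unproven effect.

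**What to change.** 1. In Table 3, set the SOC and PT numerators to patients with at least one serious adverse event in that SOC or PT, whatever the causality, over the safety analysis cases.
2. For the serious ADR table, state a separate numerator: patients with at least one serious ADR in that SOC or PT.
3. In SAP 1.1, word the risk-of-death and hospitalisation criteria for adverse events in general, to match the adverse event definition.

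Items 1 and 2 cost a few words in the SAP and one numerator in the table program. They need no new data, because seriousness and causality are already recorded separately. Item 3 is a wording change only. It makes the SAP consistent but cannot alter seriousness ratings already entered on the CRFs.

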1.2. Cases for Analysis

The unit for the cases to be analyzed is primarily based on the "Patient's Unique Number".

Terms	Definition
Registered cases	Cases registered with a date up to the data cut-off date, and the registration status is "Registered" or "Registered (No Survey)".
Continuing cases from clinical trials	Among the registered cases, cases that were registered with "Participation in Clinical Trials" as "Yes" on the registration form. In the same case, if the registration content is different, prioritize "Yes" over "No" and "Unknown".
Unknown cases (Cases where participation in clinical trials is unknown)	Among the registered cases, cases that were registered with "Participation in Clinical Trials" as "Unknown" on the registration form.
Post-marketing cases	Among the registered cases, cases that were registered with "Participation in Clinical Trials" as "No" on the registration form. In the same case, if the registration content is different, prioritize "No" over "Unknown".
Number of registered cases targeted for CRF collection	Among the registered cases, the number of cases where the first CRF was generated.
Unrecovered CRF cases	Among the target registered cases for CRF collection, cases where the CRF has not been collected.
Unobtained CRF cases	Among the target registered cases for CRF collection, cases where the CRF has not been obtained.
Recovered CRF cases	Among the target registered cases for CRF collection, cases where the CRF has been collected and the data has been fixed.
Cases excluded from safety analysis	Among the post-marketing cases of the CRF collection, cases that fall under the following items. However, even if it is a continuous case from a clinical trial, if it falls under the following 2), it will be treated as a case excluded from the safety analysis. 1) Cases where the drug has not been administered 2) Cases where the details of the administration status cannot be confirmed because the administration status of the drug is not described
Cases subject to safety analysis	Among the post-marketing cases of the CRF collection, cases excluding those excluded from the safety analysis.

Terms	Definition	
Cases excluded from efficacy analysis	Among the cases subject to safety analysis, cases that fall under the following items. 1) Cases where the purpose of use is not "suppression of ADPK progression with a rapid kidney volume increase in patients with increase kidney volume" 2) Cases where the efficacy evaluation items have not been measured after the administration of the drug, or there is no efficacy data measured with the allowable range at each evaluation time	
Cases subject to efficacy analysis	Among the cases subject to safety analysis, cases excluding those excluded from the efficacy analysis.	

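### The safety set admits only cases with trial participation recorded as No, so treated Unknown cases and documented continuing cases with a CRF are neither tabulated nor listed as excluded

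*SAP*

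**What the plan says.** **Protocol.** The target population is "All patients treated with Samsca after March 24, 2014 for the indication of" ADPKD. Registration is universal ("All patients treated with Samsca must be registered in the survey until" the approval condition is lifted), and "CRFs must be collected from all patients until the total number of patients registered in the survey" reaches the planned 1,600. A further target is at least "800 patients with long-term treatment", meaning four years or more. No exclusion by earlier trial participation appears. Hepatic dysfunction and "Safety of Samsca in ADPKD patients after long-term treatment" are named analysis items. The protocol also asks for the numbers of patients excluded and analysed for safety, without defining who is excluded.

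**SAP 1.2.** Registered cases are classified by the trial-participation item on the registration form: Yes (continuing from trials), Unknown ("Unknown cases (Cases where participation in clinical trials is unknown") and No (post-marketing). Where entries conflict, Yes takes precedence over the other two, and No over Unknown. The safety set is "Among the post-marketing cases of the CRF collection, cases excluding those excluded from the safety analysis". Exclusions are taken from the same post-marketing cases: (1) drug not administered, (2) administration status not described. One added clause treats a continuing case as excluded if it meets (2).

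**Where the set is used.** The background tables (SAP 2.2), the adverse event and ADR tables (2.3.1.1), the serious event tables (2.3.2) and the ALT/AST Kaplan-Meier analysis (2.3.2.1) all use it. The efficacy set is a subset of it, so 2.4.1 and 2.4.2 inherit the restriction. The listing in 2.1.1 covers only cases excluded from the safety and efficacy analyses.

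**The concern.** The rule selects on a registration item that has no role in the protocol's population. A treated Unknown or continuing patient can have a collected CRF with a documented hepatic event, and that event would reach no table in the supplied SAP. The loss would also be hard to see, because the patient would not be listed as excluded either. The numbers the protocol asks for need not add up: collected CRFs can exceed analysed plus excluded.

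The protocol ties its planned number to liver safety ("Depending on the onset of significant drug-induced liver injury post-marketing, the planned" number is to be re-evaluated), so it matters which patients the liver tables count. The SAP does not say whether 1,600 and 800 refer to all CRF cases or only to the safety set.

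**Working it through.** **Set logic.** Sort the cases with a collected CRF by recorded trial participation and follow each through SAP 1.2 and 2.1.1.

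| Recorded participation | In the safety set? | On the exclusion list? |
|---|---|---|
| No, treated and documented | Yes | No |
| No, untreated or status not described | No | Yes |
| Yes, status not described | No | Yes, through the added clause |
| Yes, status described | No | No |
| Unknown only | No | No |

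The last two rows belong nowhere. Hence collected - analysed - excluded = Unknown CRF cases + continuing CRF cases with described status. This is zero only if both groups are empty.

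The third and fourth rows also sit oddly together: a continuing case with poor documentation is listed, while one with good documentation is not. An exclusion clause for continuing cases has a purpose only if they could otherwise be analysed, yet the safety-set definition shuts them out.

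**Size.** The documents give no counts for the two groups and no event rate, power or precision behind 1,600, so there is no stated figure to reproduce. For illustration, let f be the share of 1,600 affected (assumed 5-20%).

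- Safety set: n = 1,600 x (1 - f).
- Exact one-sided 95% upper limit when no event is seen: 1 - 0.05^(1/n).
- Chance of at least one event at an assumed true rate of 0.1%: 1 - 0.999^n.

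| f | n | Upper limit | Chance of at least one event |
|---|---|---|---|
| 0 | 1,600 | 0.187% | 79.8% |
| 5% | 1,520 | 0.197% | 78.1% |
| 10% | 1,440 | 0.208% | 76.3% |
| 20% | 1,280 | 0.234% | 72.2% |

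The rule of three agrees: 3/1,600 = 0.19%, 3/1,520 = 0.20%, 3/1,280 = 0.23%.

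**Selection.** Suppose the kept cases have a 5% event rate and the dropped cases 0.5 to 2 times that (both assumed). The all-treated rate is 5% x [(1 - f) + f x m], where m is the ratio:

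- f = 5%: 5% x (0.95 + 0.025) = 4.88% to 5% x (0.95 + 0.10) = 5.25%
- f = 20%: 5% x (0.80 + 0.10) = 4.50% to 5% x (0.80 + 0.40) = 6.00%

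**Long-term target.** If the loss is proportional, 800 becomes 800 x 0.95 = 760 to 800 x 0.80 = 640.

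**The case against.** The strongest defence is prior exposure. A patient coming from a trial may already have taken the drug. Day 1 in the survey would then not be first exposure, early hepatic events could be under-represented, and the period before baseline in SAP 2.4 might not be drug-free. This stands as a reason to keep continuing cases out of the incidence, time-to-onset and efficacy analyses, although the SAP does not state it. It is not a reason to report nothing. It is weaker for Unknown cases, since the SAP accepts a case as post-marketing on one No entry against an Unknown one.

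Other points also stand. The protocol expects some patients to be excluded, so an all-patient survey need not put everyone in the safety set. The event tables are labelled as covering post-marketing cases, so the restriction is visible. The precedence rule limits the Unknown group to cases never recorded otherwise.

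A reader might go further than the documents allow:

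- *Unknown means a blank field.* It is a recorded answer.
- *Every Unknown case was treated and has a CRF.* The group is defined among registered cases, which include those registered without survey. The point applies only to any that were treated and have a CRF.
- *Continuing patients have the longest exposure.* No document states their earlier treatment arm, dose or duration.
- *The SAP deliberately discards all continuing cases.* The added clause leaves the intent unclear.
- *A planned long-term safety table loses its best patients.* The supplied SAP contains no such table; its absence would be a separate point.

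**Conclusion.** The point holds for treated Unknown cases with a CRF: under SAP 1.2 they are neither analysed nor listed as excluded. For continuing cases with described administration the literal result is the same, but the added clause makes the SAP inconsistent, so that part is a contradiction to resolve and not a settled decision.

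The size is unknown. Under the assumed 5-20%, precision falls only slightly (upper limit 0.19% to 0.20-0.23%). Selection and untabulated adverse events are the main issue. It is tempting to divide the 80-320 dropped patients by the 800 long-term target and report a 10-40% loss. That holds only if every dropped patient is a long-term patient, which nothing in the documents shows; a proportional loss is 5-20%.

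The conclusion rests on the supplied text. The part of the SAP before section 1.1 was not available, so a statement there about these groups cannot be ruled out.

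**What to change.** 1. Include treated Unknown cases with a CRF in the main safety set, with a sensitivity table without them. Downside: some may have had earlier exposure.
2. In the adverse event and serious adverse event tables, keep the post-marketing column and add columns for treated Unknown cases with a CRF, for continuing cases, and for the all-treated total. The post-marketing column then serves as the sensitivity result in those tables.
3. Because the efficacy set is derived from the safety set, say explicitly whether Unknown cases enter it. If efficacy and time to onset stay restricted to post-marketing cases, give prior exposure as the reason.
4. Reconcile the continuing-case clause in SAP 1.2 with the safety-set definition.
5. Report the number of CRF cases in each group, so that collected = analysed + excluded, and list every case left out under 2.1.1 with its reason.
6. State whether 1,600 and 800 count all CRF cases or only the safety set. The difference is material: keeping 1,600 in the safety set would need 1,600/0.95 = 1,685 CRF cases at an assumed 5% and 1,600/0.80 = 2,000 at 20%.

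The cost is a few table columns, one sensitivity table and a few sentences of SAP text. No new data collection is needed.
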